## 11.5 Radiology Review

The review of the baseline neuroimaging will be performed at DFCIto ensure the participants meet the inclusion criterial before the randomization. The review of on-study neuroimaging will be performed retrospectively at DFCI.

# **12. DATA REPORTING/REGULATORY REQUIREMENTS**

# 12.1 Data Reporting

The Office of Data Quality (ODQ) will collect, manage, and perform quality checks on the data for this study.

## 12.1.1 Responsibility for Data Submission

All investigative sites are responsible for submitting data and/or data forms to the ODQ according to the schedule set by the ODQ as noted in Table 7 below.

Table 7: Study Data Submission Table.

Form	Submission Timeline	
Eligibility Checklist	Complete prior to study registration	
On Study Form	Within 30 days of registration	
Baseline Assessment Form	Within 30 days of registration	
Treatment Form	Within 30 days of treatment administration	
Adverse Event Report Form	Within 30 days of AE assessment/notification	
Response Assessment Form	Within 30 days of the response assessment	
Off Treatment/Off Study Form	Within 30 days of completing treatment or being taken off study for any reason	
Follow up/Survival Form	Within 30 days of the protocol defined follow up visit date or call	

# 12.2 Data Safety Monitoring

The DF/HCC Data and Safety Monitoring Board (DSMB) will review and monitor study progress, toxicity, safety and other data from this study. The Board is chaired by a medical oncologist from outside of DF/HCC and its membership composed of internal and external institutional representation. Information that raises any questions about participant safety or protocol performance will be addressed by the Overall PI, statistician and study team. Should any major concerns arise, the DSMB will offer recommendations regarding whether or not to suspend the study.

The DSMB will meet twice a year to review accrual, toxicity, response and reporting information. Information to be provided to the DSMB may include: participant accrual; treatment regimen information; adverse events and serious adverse events reported by category; summary of any deaths on study; audit results; and a summary provided by the study team. Other information (e.g. scans, laboratory values) will be provided upon request.

# 12.3 Multicenter Guidelines

This protocol will adhere to DF/HCC Policy MULTI-100 and the requirements of the DF/HCC

Multi-Center Data and Safety Monitoring Plan. The specific responsibilities of the Overall PI, Coordinating Center, and Participating Institutions and the procedures for auditing are presented in Appendix B.

# 13. STATISTICAL ANALYSIS PLAN

This section outlines the statistical analysis strategy and procedures for the study. If, after the study has begun, changes are made to primary and/or key secondary hypotheses, or the statistical methods related to those hypotheses, then the protocol will be amended (consistent with ICH Guideline E-9). Changes to exploratory or other non-confirmatory analyses made after the protocol has been finalized, along with an explanation as to when and why they occurred, will be listed in the Clinical Study Report (CSR) for the study. Post hoc exploratory analyses will be clearly identified in the CSR.

## 13.1 Study endpoints

Efficacy and safety endpoints that will be evaluated for within- and/or between-treatment differences are listed below, followed by the descriptions of the derivations of selected endpoints.

## **13.1.1 Efficacy Endpoints**

Tumor infiltrating T cell (TIL) density is defined as the number of T lymphocytes per nucleated cell, and calculated by detailed sequencing of recombined T cell receptor sequences obtained from the tumor specimen gDNA.

PFS6 is defined as the percentage of participants with progression-free survival at 6 months from surgery as defined by RANO.

OS is defined as the time from randomization until death from any cause. Participants will be followed for survival status after progression or discontinuation of the study drug for other reasons.

## 13.1.2 Safety Endpoints

The primary safety endpoints are AEs graded using CTCAE version 5.0 criteria. Safety will be assessed by quantifying the toxicities and grades experienced by participants who have received VB-111, including serious adverse events (SAEs). Other safety endpoints include laboratory safety assessments, KPS status, vital signs and physical examinations.

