# 1. OBJECTIVES

#### 1.1 Study Design

This is a randomized, controlled, blinded, phase II, surgical trial to evaluate early immunologic pharmacodynamic parameters for the viral cancer therapy ofranergene obadenovec (VB-111) in participants with surgically accessible recurrent/progressive glioblastoma (rGBM). The principal goal of this study is to investigate if neoadjuvant VB-111 elicits a tumoral immunologic response, if the immune response can be sensitively monitored using tumor and peripheral blood immune cells, and if neoadjuvant VB-111 increases tumor-specific T cells. Please see Figure 1 for Schema.

**Group A:** VB-111 at  $1 \times 10^{13}$  VPs will be administered intravenously  $21\pm7$  days prior to surgery. Upon recovering from surgery (within 28-35 days after surgery), participants will receive intravenous VB-111 every 6 weeks. Upon evidence of contrast-enhancing progression, participants may initiate bevacizumab or biosimilar as needed for supportive care and will continue with VB-111 infusions until progression is supported by two consecutive time points of tumor growth.

**Group B:** Placebo will be administered intravenously 21±7 days prior to surgery. Upon recovering from surgery (within 28-35 days after surgery), participants will receive intravenous VB-111 every 6 weeks. Upon evidence of contrast-enhancing progression, participants may initiate bevacizumab or biosimilar as needed for supportive care and will continue with VB-111 infusions until progression is supported by two consecutive time points of tumor growth.

**Group C:** Placebo will be administered intravenously  $21\pm7$  days prior to surgery. Upon recovery from surgery, participants will receive standard of care treatment and every 6 weeks until evidence of progression is supported by two consecutive time points of tumor growth.

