# **1.2** Primary Objectives & Hypotheses

**Primary Objective 1:** To evaluate the influence of VB-111 on tumor infiltrating T lymphocyte (TIL) density in recurrent/progressive GBM participants.

We hypothesize that neoadjuvant VB-111 will increase tumor infiltrating T lymphocytes within the tumor and enhance systemic tumor-specific T cell responses compared to adjuvant and control tumors.

**Primary Objective 2:** To evaluate the safety and tolerability of intravenous VB-111 in progressive/recurrent GBM participants undergoing surgery.

Safety analysis will be based on toxicities and grades as defined by CTCAE version 5.0 criteria, including serious adverse events (SAEs). The attribution to drug, time-of-onset, duration of the event, resolution, and any concomitant medications administered will be recorded. AEs analyzed include but are not limited to all AEs, SAEs, and fatal AEs.

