#### 5.7.5 Cerebral Edema

Due to the immunologic nature of VB-111, cerebral edema may theoretically result due to immune infiltration of the brain. Symptoms related to cerebral edema may include headache or neurologic deficit that is either new or worsened. Participants with any signs or symptoms of cerebral edema should be treated as clinically appropriate, including initiation or increased systemic corticosteroid dosing, initiation of bevacizumab or biosimilar, treatment with an osmotic diuretic, or surgical decompression.

Bevacizumab or biosimilar may be used to control edema, mass effect, or as a steroid-sparing agent for as long as the treating investigator deems clinically necessary. Treatment with additional VB-111 may be re-initiated if clinically significant symptoms attributable to cerebral edema have resolved to grade  $\leq 1$  or pre-treatment baseline or after discussion with the Overall Principal Investigator. A washout period of 2 weeks between VB-111 and bevacizumab or biosimilar doses is recommended. Participants who develop CTCAE 5.0 grade 4 cerebral edema attributable to VB-111 should not receive further doses and should discontinue study therapy.

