- 8. A contact/visit is to be performed at 30 days (+7 days) after the last study drug is given. This may be performed via documented phone conversation with a study nurse or clinician or a clinic visit. All participants will be followed until resolution or stabilization of any serious or reportable adverse events occurring during treatment or starting within 30 days of last study drug.
- 9. For participants who discontinue study treatment for reasons other than disease progression, every effort should be made to continue monitoring their disease status by radiologic imaging at a schedule developed by the treating investigator until (1) documented disease progression, (2) death or (3) the end of the study, whichever occurs first.
- 10. Long Term Follow Up: participants will be followed every 3 months (+/- 1 month) via contact or medical record review until death for post-treatment therapies, reason for stopping those therapies and survival.
- 11. Informed Consent must be obtained by a delegated MD attending. No study specific screening procedures may occur until after the informed consent process is complete. Informed Consent may be obtained within 28 days of enrollment.
- 12. Background information/history is to include review of treatment history for GBM, any ongoing medical conditions and medical history pertaining to eligibility on study and involvement during study.
- 13. Inclusion/exclusion criteria: source documentation providing investigator's confirmation that the participant meets all eligibility criteria must be available prior to registration.
- 14. Vital signs include weight, heart rate, blood pressure, respiration rate, temperature. Vital signs must be performed prior to administration of treatment on treatment days. Height required only at screening.
- 15. Neurologic Exam is to be completed by the investigator or qualified designee at screening, and Day 1 of postsurgery treatment cycles.
- 16. Directed Physical Exam is to be completed at screening, pre-surgery treatment visit, Day 1 of post-surgery treatment cycles, and as clinically indicated by the investigator or qualified designee.
- 17. Performance Status is to be assessed by KPS (Appendix A).
- 18. Concomitant medications and reason for administration should be documented in the case history from date of consent up to the 30-Day Post Drug Visit. Concomitant medications administered after 30 days after the last dose of trial treatment should be recorded for SAEs.

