inflammatory changes that may include edema. Therefore, radiographic progressive disease will be defined by assessment of enhancing tumor and will not declare tumor progression based on the presence of T2 or FLAIR changes alone as outlined in RANO because:

- There is no expectation that immunotherapy agents will falsely diminish enhancing tumor burden as has been noted with anti-angiogenic therapies; and
- Immune based therapies are expected to induce inflammatory responses which may be associated with increased edema and T2/FLAIR changes. Such radiographic finding may inaccurately be interpreted to represent tumor progression (i.e. pseudoprogression).

In participants who have initial evidence of radiographic PD, it is at the discretion of the treating physician whether to continue a participant on study treatment for up to three months pending confirmation of PD on follow-up imaging. This clinical judgment decision should be based on the participant's overall clinical condition, including performance status, clinical symptoms, and laboratory data. Participants may receive bevacizumab or biosimilar 10mg/kg2 every 2 weeks in addition to study treatment while waiting for confirmation of PD if they are not experiencing significant clinical decline and the participant is adequately tolerating study therapy (if a participant is required to discontinue study treatment for toxicity as defined per protocol section 5, then they must be taken off-treatment).

When feasible, study therapy should not be discontinued until progression is supported by two consecutive time points of tumor growth. This allowance to continue treatment despite initial radiologic progression takes into account the observation that some participants can have a transient tumor flare in the first few months after the start of immunotherapy, but with subsequent disease response [49]. Participants that are exhibiting significant neurologic decline are not required to have repeat imaging for confirmation of progressive disease.

A randomized, placebo controlled phase II, surgical trial to evaluate early immunologic pharmacodynamic parameters for the viral cancer therapy ofranergene obadenovec (VB-111) in patients with surgically accessible recurrent/progressive glioblastoma Version 3.0 February 18, 2021

able 0. illiagi	able 6: Imaging and Treatment After 1st Radiographic Evidence of PD.							
	No Significant Neuro	ologic Decline	Significan	Significant Neurologic Decline				

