## 13.5 Safety Analyses

Safety and tolerability will be assessed by clinical review of all relevant parameters including adverse experiences (AEs), laboratory tests, and vital signs. Safety summaries will be reported for both cohorts. Death (other than death related to progressive disease) that occurs within 30 days of VB-111 administration will lead to pausing of the study and analysis of the toxicity data.

Adverse experiences (specific terms as well as system organ class terms) and predefined limits of change in laboratory, and vital sign parameters that are not pre-specified as events of interest will be summarized with descriptive statistics (counts, percentage, mean, standard deviation, etc.).

Continuous measures such as changes from baseline in laboratory, and vital signs parameters that

are not pre-specified as events of interest will be summarized using descriptive statistics (mean, standard deviation, etc.) for baseline, on-treatment, and change from baseline values.

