# **13.9** Extent of Exposure

Extent of Exposure for a participant is defined as number of cycles in which the participant receives

the study medication infusion. Summary statistics will be provided on Extent of Exposure for APaT population.

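### Cheap, low-priority improvement: the planned AE summaries for Primary Objective 2 do not show VB-111 without bevacizumab, and the date needed to separate the two is optional on the CRF

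*Combined protocol and SAP*

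**What the plan says.** **Safety analysis.** Section 1.2 makes the safety and tolerability of intravenous VB-111 the second primary objective. Section 13.1.2 defines how: "Safety will be assessed by quantifying the toxicities and grades experienced by participants who have received VB-111". The analysis set in 13.2 is everyone with at least one dose of study treatment. Section 13.5 says "Safety summaries will be reported for both cohorts", although the trial has three groups, and describes the AE summaries as descriptive statistics such as counts and percentages. Section 13.9 measures exposure in cycles only: "Extent of Exposure for a participant is defined as number of cycles in which the participant receives" the study infusion.

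**Bevacizumab in Groups A and B.** There are three routes.
- At contrast-enhancing progression, section 1.1 says "participants may initiate bevacizumab or biosimilar as needed for supportive care and will continue with VB-111 infusions until progression" is confirmed at a second time point.
- While confirmation is awaited, section 11.4 says "Participants may receive bevacizumab or biosimilar 10mg/kg2 every 2 weeks in addition to study treatment while waiting for confirmation of PD".
- For symptoms, section 5.7.5 says "Bevacizumab or biosimilar may be used to control edema, mass effect, or as a steroid-sparing agent". This route does not require progression.

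**What is recorded.** Section 1.2 says "The attribution to drug, time-of-onset, duration of the event, resolution, and any concomitant medications administered will be recorded". Footnote 18 of the Study Calendar says "Concomitant medications and reason for administration should be documented in the case history". Section 5.7.1 puts all concomitant medication on the CRF, but where medication changes during the trial it permits the date rather than requiring it, and only when the information is available. By contrast, footnote 30 of the Study Calendar asks for start and stop dates of therapies given after the end of treatment. Section 13.7 summarizes concomitant therapies by treatment.

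**The concern.** In Groups A and B, bevacizumab is a foreseeable second active drug with its own written rules. In the planned summaries, an event that starts after the first bevacizumab dose counts the same as one that starts on VB-111 alone. The summary of concomitant therapies by treatment does not link bevacizumab use to AE onset. Group C is not a bevacizumab-free reference either, because Table 1 allows bevacizumab as a standard-of-care choice.

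The protocol itself treats the distinction as important. Section 2.2.2 suggests that lack of VB-111 monotherapy priming may explain why the phase 3 trial, which gave the two drugs together, did not repeat the phase 2 result. Sections 5.7.3 and 5.7.5 recommend a two-week washout between doses of the two drugs. The AE list in 7.1.1 draws on about 180 patients from phase 1 and 2 trials and 126 from the phase 3 combination trial, without separating them. This trial could add a cleaner view, but its planned summaries do not provide one.

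What is at stake is how informative the answer to a primary objective will be. The TIL analysis and the rule in 13.5 that pauses the study after certain deaths are unaffected.

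**Working it through.** The documents give no rate, precision target or sample size for the safety objective, so there is no figure to reproduce. The check has four parts.

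**1. Is there a split anywhere?** Sections 13.1.2, 13.2, 13.5, 13.6 and 13.9 contain no cut of AEs or exposure at the first bevacizumab dose. They also contain no summary of the pre-operative window, which is the only blinded, randomized comparison of VB-111 with placebo.

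**2. How much AE-collection time could fall after bevacizumab start?** Inputs:
- VB-111 every 6 weeks from adjuvant Cycle 1 Day 1 (day 0), so on days 0, 42, 84 and so on (5.1).
- AE collection to 30 days after the last infusion (7.5).
- First progression at day 83, the phase 2 median PFS in the primed-combination group (2.2.2). That this runs from Cycle 1 Day 1, and that bevacizumab starts on the same day, are assumptions.
- MRI every 6 weeks, with VB-111 stopped once the second consecutive MRI confirms progression (5.1). First progression near day 84 and confirmation near day 126 leave one further dose, on day 84.

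Share = (end of AE collection − 83) / end of AE collection.
- End of collection: 84 + 30 = 114.
- Share: (114 − 83) / 114 = 31/114 = 27%.

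For Group A counted from the neoadjuvant dose, add the time from that dose to Cycle 1 Day 1. This is 14 + 28 = 42 days at the shortest and 28 + 35 = 63 days at the longest.
- 31 / (114 + 42) = 31/156 = 20%.
- 31 / (114 + 63) = 31/177 = 18%.

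The shares rise only if VB-111 continues longer, through later confirmation, a non-confirming scan or an exception under 11.4:
- Last dose day 126: (156 − 83) / 156 = 73/156 = 47%.
- Last dose day 168: (198 − 83) / 198 = 115/198 = 58%.

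These are shares of time, not of events.

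**3. How far could a pooled AE rate move?** This needs figures that the documents do not give. Let p be the AE risk on VB-111 alone, f the share of participants who add bevacizumab, and q the added risk on the combination. Then the pooled rate is 1 − (1 − p)(1 − f·q). With p = q = 10%, all assumed:
- f = 25%: 1 − 0.90 × 0.975 = 12.25%.
- f = 50%: 1 − 0.90 × 0.95 = 14.5%.
- f = 75%: 1 − 0.90 × 0.925 = 16.75%.

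Among the 30 participants in A and B this is about 3.7, 4.4 and 5.0 with the event, against 3.0 on VB-111 alone. The result depends on f and q, and both are unknown.

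**4. Would a simple before/after cut be enough?** No. Group B receives placebo before surgery and no VB-111 until 28 to 35 days after it. With bevacizumab at day 83, its time before bevacizumab is 42 + 83 = 125 to 63 + 83 = 146 days. Of this, 42/125 = 34% to 63/146 = 43% is placebo, surgery and recovery. A two-period table would mix that time with VB-111 time, so more periods are needed.

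**The case against.** The other side has a good case. Bevacizumab is written into the protocol as supportive care, and the objective concerns participants undergoing surgery, not VB-111 in isolation. Reporting AEs for the strategy as delivered is therefore a legitimate answer. Section 13.5 does not fix table layouts, so a listing by period could be produced without contradicting it. Attribution to drug is recorded on a five-point scale (7.2), which is the existing means of separating drug effects. The CRF fields are not shown, and sites need dose dates to follow the recommended washout, so the dates may well be captured already.

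Most of this stands, and it lowers the priority. A reader might infer that VB-111 safety without bevacizumab cannot be recovered from this trial. The documents do not support that: AE onset, concomitant medications and attribution are recorded, so a split is probably derivable.

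Two things remain. Attribution is an investigator's judgement and does not replace a division by time. And the protocol text, as opposed to CRFs we cannot see, leaves the date of a medication change optional, while both the split and its exposure time depend on that date.

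**Conclusion.** The point holds as a cheap, low-priority improvement. The planned summaries pool all AEs in VB-111 recipients and do not show VB-111 without bevacizumab, and 5.7.1 does not require the date that would allow the separation.

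The size is uncertain because bevacizumab uptake is not given. On the path where progression is confirmed at the next scheduled MRI, about 27% of post-operative AE-collection time follows bevacizumab start, or 18% to 20% for Group A from the neoadjuvant dose. This rests on first progression and bevacizumab start both at day 83. With low uptake, little mixing occurs. The number of AEs affected cannot be computed from the documents.

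Two stronger readings should be resisted.
- From the 10% historical PFS6 in 13.4, a reader might infer that about 27 of 30 participants in A and B (30 × 0.90) would be affected. That figure counts progression or death by 6 months, not bevacizumab use.
- From the Appendix C coversheet, which asks about a second regimen only for post-surgery Group C, a reader might infer that bevacizumab goes uncaptured in A and B. The coversheet travels with a MedWatch form, and all AEs also go on the toxicity CRFs (7.11). The fields of those forms are not shown, so no change to Appendix C is warranted.

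**What to change.** 1. In 5.7.1, make the date of every bevacizumab or biosimilar dose mandatory on the CRF.
2. In 13.5, add one descriptive AE table by period of onset:
   - period 1: blinded pre-operative dose to surgery, Group A versus Groups B and C combined;
   - period 2: surgery to first adjuvant VB-111 dose;
   - period 3: adjuvant VB-111 before any bevacizumab, Groups A and B;
   - period 4: after the first bevacizumab dose, Groups A and B.

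   If bevacizumab starts before period 3 would begin, period 4 starts at that dose. Give the number of participants and the exposure time in each period. Label the contrast of periods 3 and 4 as non-randomized and confounded with progression.

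The pooled summary of the strategy as delivered can stay. The cost is one mandatory date field and one extra table with small numbers per cell. The table describes the periods. It cannot isolate a causal effect of VB-111.
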